# 3.3.3 Allocation Concealment and Blinding

Allocation concealment is ensured as the kits will be assigned in chronological order on the basis of the confirmed subject eligibility. Randomization will occur individually, each kit will be assigned to a unique randomized subject and the simultaneous randomization of groups of subjects will be prevented.

All attempts will be made to keep the study team, site staff and subjects blinded to study treatment throughout the study, including:

Members of the study team or site staff will not have access to the randomized treatment assignment.

Study drug will have similar appearance, packaging and use instructions as the corresponding vehicle.

# 3.3.4 Prior and Concomitant Therapy

### 3.3.4.1 Definition

Information on previous and concomitant therapies will be collected and recorded in the CRF.

Previous therapies are defined as medications or procedures that have been stopped before the Screening visit and includes all acne therapies (within 6 months) and all other therapies (within 1 month).

Concomitant therapies are defined as:

- any existing therapies ongoing at the Screening visit;
- any changes to existing therapies (such as changes in dose or formulation) during the course of the clinical study, or

any new therapies received by the subject since the Screening visit

Any new concomitant therapy or modification of an existing therapy may be linked to an adverse event (AE). A corresponding AE form must be completed to account for the change in therapy, except in some cases such as therapy used for prophylaxis, dose modification for a chronic condition, etc. In these cases, the medication will be linked to an item in the medical history.

### 3.3.4.2 Categories

The following two categories are to be considered for previous and concomitant therapies:

- Drugs/therapies including, but not limited to, prescription, over-the-counter (OTC), birth control pills/patches/hormonal devices, vitamins, cleansers, moisturizers, sunscreens, herbal medicines/supplements, and homeopathic preparations.
- Medical and surgical procedures including, but not limited to, laser/radiation procedures, dermal fillers, X-rays (excluding dental X-rays), etc.

### 3.3.5 Treatment Compliance - Primary Source Data

Subjects will be instructed by study personnel on the importance of being compliant with the use of the study drug and non-study products.

Subjects will receive an electronic tablet at baseline for recording study medication use on each half-face (electronic dosing calendar) with clear instructions for daily use throughout the study (see Section 3.1.2). The subject-reported data in the dosing calendar will be used as the primary source data for calculating treatment compliance, per each half-face.

Results are uploaded to a secure portal for remote monitoring, with subject counseling, as needed, throughout the study.

Subjects will be instructed to return the study electronic tablet and all study medication at each study visit. Site personnel will review dosing compliance data since the last visit, derive treatment compliance for each half-face and counsel/re-train subjects, if needed. Treatment compliance will be derived from the total expected doses and number of actual doses recorded, over a given visit interval.

Any missed dose will be considered a protocol deviation, based on recordings in the dosing calendar. Subjects should be appropriately counseled on the importance of following study drug dosing instructions and daily recordings in the dosing calendar. Subjects should be reminded and encouraged to follow guidelines for non-study product use, throughout the study.

### 3.3.6 Treatment Compliance - Supportive Video Evidence

The assigned electronic tablet will also be used by subjects to capture videos of study drug application, for each half-face, on a daily basis (Protocol section 5.4.3 - Study Drug Application with Video Collection). The study drug label will be apparent in the video to confirm which product was applied to each side of the face (e.g., red label = right side of face, etc). All videos are collected

CD5789.SPR202395.SAP.V02 - Final Version 27F

and stored locally and securely on the electronic tablet. There are no video uploads or transfer from the local device. Only designated site staff will have access to view these videos on the electronic tablet.

Even though no videos will be uploaded to a central portal for remote viewing, the electronic dosing calendar will include a question whether the subject is collecting daily videos, which site staff can reference for remote monitoring and counseling.

While the dosing calendar data will be the primary source for reporting treatment compliance, daily videos are used for site staff to spot-check for proper use of study medication, and appropriately counsel and re-train subjects on the importance of following proper study drug instructions.

At each visit, the subject will return the electronic tablet. Site staff will review videos and provide subject counseling and reminders on the importance of following study drug dosing instructions, throughout the study. At least two videos since the prior visit should be reviewed. Subjects who display repeated non-compliance based on video evidence, despite repeated counselling and retraining, should be discontinued from the study, based on investigator discretion.

Note: Subjects will be informed that videos will be reviewed to ensure proper use of study drug throughout the study; however, they will not be told how many videos will be reviewed. This non-disclosure allows subjects to be appropriately informed with sufficient detail of what study procedures will be performed and does not create any added risks to the subjects by withholding this level of detail. Preserving the notion that someone is watching is considered critical to maintaining the integrity of the split-face study design, as it provides motivation to remain compliant, while attempting to balance the administrative burden of daily video review by site staff, over a total treatment period of approximately 170 days, for each subject. The subject-reported dosing compliance data recorded on the electronic dosing calendar will be used to derive compliance, which is a common procedure used in clinical studies to reliably assess daily product use. Repeated non- compliance observed by video evidence should result in subject termination, based on investigator discretion.

At the end of the study, the electronic tablet will be collected, and all collected information fully removed by the clinical site and confirmed by the equipment vendor.

# 3.4 Duration of Subject Participation

The expected duration for each subject's participation in the study is approximately 28 weeks (including a 4-week screening period and a 24-week treatment period).

### 3.4.1 Early Termination Visit

When a subject does not complete the clinical study, he/she will be fully assessed, if such assessment is possible. The procedures designated for the Week 24/Early Termination visit should be completed for all subjects discontinuing the study and the appropriate CRF page should be completed.

CD5789.SPR202395.SAP.V02 - Final Version 27F

Refer to section 3.2.4 for reasons for study discontinuation.

### 3.4.2 Unscheduled Visit

The subject should be reminded to adhere to the study visit schedule. Unscheduled visits are unplanned and may include examinations for safety or repeat study assessments. Visits occurring outside of the visit window are not considered unscheduled visits.

Assessments to be conducted at the unscheduled visit will depend on the reason for the visit. Any of the procedures/assessments listed in section 3.1.2 in may be conducted, as appropriate.

# 3.5 Efficacy and Safety Assessments

### 3.5.1 Efficacy Assessments

[figure not shown]
Efficacy measurements should be conducted by the investigators (or designees) or by subjects (for subject-reported assessments) according to section 3.1.2.

Evaluators must complete standardized training prior to performing the following assessments: atrophic scar severity (SGA), atrophic scar counts, acne severity (IGA), inflammatory lesion counts (papules and pustules), non-inflammatory lesion counts (open and closed comedones), and other lesion counts (nodules and cysts).

### Notes:

- 1) Scar severity grading (SGA) and scar counts will be performed separately. The scar severity assessment will be performed before the scar counting.
- 2) Acne severity grading (IGA) and acne lesion counts will be performed separately. The acne severity assessment will be performed before the acne lesion counting.

[figure not shown]
Throughout the study when possible, the same evaluator should perform the SGA, scar counts, IGA and acne lesion counts, for each subject. In the event there is a change in the assigned evaluator for a given subject, the reason for change should be documented. If it is not possible to use the same evaluator to follow a given subject, evaluations between the primary and subsequent evaluator should overlap (both evaluators should examine the subject together and discuss findings) for at least one prior visit. At the final study visit (Week 24 or Early Termination), attempts should be made for the rater to be the same as baseline for the following assessments, to the extent possible:

[figure not shown]

[figure not shown]
For all efficacy assessments, the zone in the middle of the face (approximately 2 cm wide and inclusive of the nose) should be excluded for clinical efficacy evaluation because subjects may apply a mix of investigational products in this area (Figure 2).

1.0

Study Number 202395 CONFIDENTIAL Page 24 of 59
Statistical Analysis Plan Final version 2.0, 27FEB2023

[figure not shown]

# 3.5.2 Safety Assessments

Safety assessments include the recording of adverse events and local tolerability scores.

### 3.5.2.1 Adverse Events

Adverse events (AEs) are to be monitored throughout the course of the clinical study. All AEs are to be reported on the Adverse Event Form with complete information as required. If AEs occur, the main concern will be the safety of the subjects. At the time of the ICF signature, each subject must be provided with the name and phone number of clinical study center personnel for reporting AEs and medical emergencies.

### 4 SAMPLE SIZE CONSIDERATION

The sample size calculation is based on the results of the study RD.06.SPR.118295 "A Multi-Center Study to evaluate Subject Reported Outcomes with use of trifarotene 50  $\mu$ g/g cream in the treatment of moderate facial and truncal acne vulgaris" and of the study RD.03.SPR.105061 "Effect of Adapalene 0.3% - Benzoyl Peroxide 2.5% gel versus vehicle gel on the risk of formation of atrophic acne scars in moderate to severe acne subjects".

In study RD.06.SPR.118295, the following results were obtained for the absolute change from baseline in total atrophic acne scar count at week 24:

These results refer to a whole face treatment whilst in the current study a split-face design is used. Moreover, due to the lack of a Vehicle arm, it is not possible to estimate the mean value and the variability of the difference in mean absolute change from baseline in total atrophic acne scar between treatment arms.

It is possible to hypothesize that the mean reduction in trifarotene 50  $\mu$ g/g cream arm when only half-face is treated is -1.7 but there are no data for estimating the variability of the difference between trifarotene 50  $\mu$ g/g cream and vehicle cream.

In study RD.03.SPR.105061 a split-face design was used and the following results were obtained for the absolute change from baseline in total atrophic acne scar count at week 24:

CCI

Under the following hypotheses:

- Mean absolute change from baseline in total atrophic acne scar count at week 24 for trifarotene 50 μg/g cream is -1.7
- Mean absolute change from baseline in total atrophic acne scar count at week 24 for Vehicle cream is zero
- Difference absolute change from baseline in total atrophic acne scar count at week 24 between trifarotene 50 μg/g cream and vehicle cream is -1.7
- Variability of the difference between trifarotene 50 μg/g cream and vehicle cream is 6.0 (derived by supposing an increase of about 35% of the variability observed in study RD.03.SPR.105061)

the sample size for a Student's t-test for paired samples can be calculated according to the following formula:

$$n \ge \frac{\left(t_{\frac{1-\alpha}{2},n-1} + t_{1-\beta,n-1}\right)^2 \sigma_{Diff}^2}{\left(\mu_{Trifarotene} - \mu_{Vehicle}\right)^2}$$

where  $t_{p,v}$  is the Student's t distribution quantile with v degrees of freedom and probability p (n is rounded up to the closest integer).

**Table 8 Sample Size Calculation** 

α (2-sided)	β	Power (%)	μ Trifarotene - μ Vehicle	♂ Diff	n	Drop-out and Non-evaluable Proportion (%)	Subjects to be Randomized
0.05	0.2	80	-1.7	6.0	100	15	118

An initial number of 118 subjects is planned to be randomised. Due to the uncertainty of the estimation of the variability, a blinded sample size re-estimation will be performed after 40 subjects complete/discontinue the study (i.e. after 33% of the initial planned subjects complete/discontinue the study) in order to evaluate the need for additional subjects to be randomized.

### 4.1 Blinded Sample Size Re-estimation

A blinded sample size re-estimation will be performed after 40 subjects complete/discontinue the study (i.e. after ~33% of the initial planned subjects complete/discontinue the study) in order to evaluate the need for additional subjects to be randomized.

Given the paired-sample problem of testing the following two-sided hypothesis

Study Number 202395 Statistical Analysis Plan CONFIDENTIAL

Page 32 of 59 Final version 2.0, 27FEB2023

$$\begin{cases} H_0: \mu_{Diff} = 0 \\ H_a: \mu_{Diff} \neq 0 \end{cases}$$

for the mean of difference between paired samples with unknown variance of difference  $\sigma_{Diff}^2$ , the initial sample size per group  $N_{init}$  is determined on the basis of the anticipated estimate of variance of difference  $S_{init}$  and the expected mean of difference  $\mu_{Diff}$ = $\delta$  under  $H_a$  as follows:

$$N_{init}(S_{init}) \ge \left(t_{1-\frac{\alpha}{2},N_{init}-1} + t_{1-\beta,N_{init}-1}\right)^2 \frac{S_{init}^2}{\delta^2}$$

After n1<Ninit pairs of observations, the sample size is recalculated by replacing the initial estimate of variance of difference Sinit with the variance estimate Srecalc from the subsample in the sample size formula:

$$N_{recalc}(S_{recalc}) \ge \left(t_{1-\frac{\alpha}{2},N_{recalc}-1} + t_{1-\beta,N_{recalc}-1}\right)^{2} \frac{S_{recalc}^{2}}{\delta^{2}}$$

with the restriction that the recalculated sample size should not be lower than the initially planned one  $(N_{init})$  and should not be greater than a maximum predefined sample size  $(N_{max})$ :

$$N = min(N_{max}, max(N_{init}, N_{recalc}))$$

For this study, Nmax is set to 160 subjects.

The response variable for each subject is the within-subject difference between the observations of each treatment

$$D_j = X1_j - X2_j$$

that cannot be calculated without unblinding the treatment assigned to each half face.

If treatments assignment were known, the observed variance after n1 subjects would be calculated as follows:

$$S_{Obs}^2 = \frac{1}{n_1 - 1} \left( \sum_{j=1}^{n_1} (D_j - \overline{D})^2 \right)$$

where

$$\overline{D} = \frac{1}{n_1} \sum_{j=1}^{n_1} D_j$$

The observed variance after  $n_1$  subjects can be re-written as follows:

$$S_{Obs}^{2} = \frac{n_{1}}{n_{1} - 1} \frac{1}{n_{1}} \left[ \sum_{j=1}^{n_{1}} (D_{j} - \overline{D})^{2} \right] = \frac{n_{1}}{n_{1} - 1} \left( \overline{D^{2}} - \overline{D}^{2} \right)$$

where

Study Number 202395 Statistical Analysis Plan

### **CONFIDENTIAL**

Page 33 of 59 Final version 2.0, 27FEB2023

$$\overline{D^2} = \frac{1}{n_1} \sum_{j=1}^{n_1} D_j^2$$

is the mean of squared differences. Without unblinding the treatment assigned to each half face, we can calculate the Left-Right difference as follows:

 $LR_i = XLeft_i - XRight_i$ 

Since

$$|LR_i| = |D_i|$$

the mean of squared differences can be re-calculated as follows:

$$\overline{D^2} = \frac{1}{n_1} \sum_{j=1}^{n_1} D_j^2 = \frac{1}{n_1} \sum_{j=1}^{n_1} LR_j^2 = \overline{LR^2}$$

and the following conditions hold for the mean of differences and the squared mean of differences

 $-\overline{|LR|} \le \overline{D} \le \overline{|LR|}$ 

and

$$0 \le \overline{D}^2 \le \overline{|LR|}^2$$

where

$$\overline{|LR|} = \frac{1}{n_1} \sum_{i=1}^{n_1} |LR_i|$$

is the average of the absolute values of the Left-Right differences.

According to the previous formulas, the following boundaries can be calculated for observed variance after n1 subjects:

$$\frac{n_1}{n_1-1} \Big(\overline{LR^2} - \overline{|LR|}^2\Big) \leq S_{Obs}^2 \leq \frac{n_1}{n_1-1} \overline{LR^2}$$

The observed variance after  $n_1$  subjects can be estimated as follows:

$$S_{Obs}^2 = \frac{n_1}{n_1 - 1} \overline{LR^2}$$

Missing squared differences of atrophic acne scar counts between the left and right sides of the face at Week 24 will be imputed using multiple imputation methodology (as specified in section 6.3.6.2). A linear regression model will be used with covariates for non-missing squared differences of atrophic acne scar counts between the left and right sides of the face from earlier scheduled time points including baseline.

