# 2.2 Study Endpoints

# 2.2.1 Primary Endpoint

Absolute change from Baseline in total atrophic acne scar count per half-face at Week 24

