### 6.3.3 Analysis of Primary Endpoint

The hypothesis test for the primary endpoint can be formally defined as follows:

$$\begin{cases} H_0: \mu_{Diff} = 0 \\ H_a: \mu_{Diff} \neq 0 \end{cases}$$

where  $\mu_{Diff}$  is the mean of the differences in change from baseline in total atrophic acne scar count at Week 24 between the trifarotene 50  $\mu$ g/g side and the vehicle side.

The hypothesis test for the primary endpoint will be evaluated on the ITT population at the two-sided significance level  $\alpha = 0.05$ . Efficacy will be claimed if the between treatment difference on the primary endpoint is statistically significant with a p-value < 0.05.

The bilateral difference between the trifarotene side and the vehicle side in absolute change from baseline in total atrophic acne scar counts at Week 24 will be analyzed on the ITT population using the Student's t-test for paired samples. The point estimate of the mean difference and the related 95% confidence interval will be presented. Assumption of normality will be checked. If normality assumption is not met, the appropriate non-parametric statistical method (Wilcoxon signed rank test, Hodges-Lehmann estimate of location shift and asymptotic confidence interval) will be used.

For analysis of change from baseline in total atrophic acne scar counts to Week 24, missing counts will be imputed using Multiple Imputation (MI) under the Missing At Random (MAR) assumption. It is expected that the pattern of missing data will be monotonic, with slight deviations being corrected by the Markov Chain Monte Carlo (MCMC) method of the SAS MI procedure. Separate imputations by treatment group will be carried out. Linear regression will be employed to model the missing acne counts, with the following covariates included in the imputation model: non-missing total atrophic acne scar counts from earlier time points (see Section 6.3.6.2 for further details).

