### 6.3.6.2 Handling of Dropouts or Missing Data

Missing data for atrophic acne scar counts will be imputed using Multiple Imputation (MI) under the Missing At Random (MAR) assumption. The following steps will be followed:

- 1. The missing data pattern of atrophic acne scar counts will be evaluated. If the pattern is non-monotone, the MCMC method of SAS PROC MI will be used to make it monotone. The single chain method will be used, with 200 burn-in iterations and 100 iterations between imputations. In case of lack of convergence with the single chain method, the multiple chain method will be used. Separate imputations by treatment group will be carried out. The minimum values for imputed variables will be set to 0, in order to force PROC MI to redraw another value for imputation when an intended imputed value is less than the 0. Imputed values will be rounded to the nearest integer. The seed number will be set to 202395 and fifty (50) imputations will be created.
- 2. SAS PROC MI will be used for imputing missing values of data with monotone missing pattern. If the MCMC method of step 1 was previously employed, one imputation will be made using each of the fifty (50) MCMC-imputed datasets. If the MCMC method of step 1 was not previously employed, fifty (50) imputations will be created assuming the data are Missing At Random. The seed number will be set to 202395. A linear regression model will be used with covariates for non-missing atrophic acne scar counts from earlier scheduled time points

including baseline. In case of lack of convergence with linear regression model, a predictive mean matching method will be used. Separate imputations by treatment group will be carried out. The minimum values for imputed variables will be set to 0, in order to force PROC MI to redraw another value for imputation when an intended imputed value is less than the 0. Imputed values will be rounded to the nearest integer. Absolute and percent change from baseline in atrophic acne scar counts will be derived from the corresponding imputed lesion counts.

- 3. The imputed datasets will be analyzed as specified in sections 6.3.3 and 6.3.5.
- 4. The resulting analysis on the imputed datasets will then be combined to produce a single set of statistics using PROC MIANALYZE.

The number of fifty (50) imputations was selected in order to prevent a power falloff due to choosing a number of imputations too small [1].

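### SAP 4.1 blinded re-estimation: the variable is undefined and imputed as raw counts although the endpoint is change from baseline, and the recalculated N carries no dropout allowance

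*SAP*

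**What the plan says.** **Endpoint scale.** SAP 2.2.1 gives the primary endpoint as "Absolute change from Baseline in total atrophic acne scar count per half-face at Week 24". SAP 4 plans on the same scale: "Difference absolute change from baseline in total atrophic acne scar count at week 24 between trifarotene" and vehicle is -1.7, with SD 6.0. SAP 6.3.3 states that the tested parameter "is the mean of the differences in change from baseline in total atrophic acne scar count at Week 24" between the two sides.

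**Re-estimation.** SAP 4.1 takes over delta and the planning SD and defines D_j = X1_j - X2_j. It describes X only as the observation under each treatment. Treatment is blinded, so it uses left minus right, LR_j, and takes the upper bound n1/(n1-1) x mean(LR²) as the variance. Then comes the only sentence that says what LR is made of: "Missing squared differences of atrophic acne scar counts between the left and right sides of the face at Week 24 will be imputed". The covariates are the same quantity "from earlier scheduled time points including baseline". The cited method, SAP 6.3.6.2, works differently: it imputes counts, "Separate imputations by treatment group will be carried out", and "Absolute and percent change from baseline in atrophic acne scar counts will be derived from the corresponding imputed lesion counts".

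**Units of N.** Table 8 obtains n = 100 from the formula and adds 15% for dropout and non-evaluability: "An initial number of 118 subjects is planned to be randomised". SAP 4.1 sets N = min(N_max, max(N_init, N_recalc)) with N_max = 160 subjects. N_recalc comes from the formula that gave 100, with no 15% term. N_init is defined by that formula (100) but is also called the initially planned size (118).

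**The concern.** The re-estimation exists because the SD of 6.0 is uncertain. Its one job is to return the right N when the true SD is larger.

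- **Scale.** A variance of raw-count differences includes baseline asymmetry between the half-faces, which the change score removes. Baseline as a covariate makes sense only for raw counts, because a change-from-baseline difference at baseline is zero for everyone. Followed literally, some or all of the variance is on a scale that does not match delta.
- **Units.** A figure in evaluable pairs is compared with a floor and a cap that appear to be in randomised subjects. Whenever N_recalc exceeds the floor and is not capped, the trial would randomise the number it needs to evaluate, leaving nothing for dropout.

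**Working it through.** **1. The plan's own figure.** Inputs from SAP Table 8: alpha 0.05 two-sided, power 80%, delta 1.7, SD 6.0, dropout 15%. Solving n >= (t[0.975, n-1] + t[0.80, n-1])² x 36 / 2.89 iteratively gives n = 100 (noncentral-t power 80.1%). Then 100/0.85 = 117.6, so 118. Both figures reproduce.

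**2. Expected N under the SAP 4.1 rule.** The uncentred estimator has expectation (40/39) x (SD² + 1.7²). At SD 6.0 this is (40/39) x 38.89 = 39.89, which gives N_recalc = 111. Floor 118 and cap 160 are then applied. Power is noncentral-t for the paired test at a true difference of 1.7.

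| True SD | N_recalc | N by rule | Power, 85% evaluable | Power, all contribute | N with /0.85 | Power with /0.85, 85% evaluable |
|---|---|---|---|---|---|---|
| 6.0 | 111 | 118 | 80.1% | 86.3% | 131 | 84.1% |
| 6.5 | 128 | 128 | 77.2% | 83.6% | 151 | 83.6% |
| 7.0 | 147 | 147 | 76.9% | 83.3% | 160 | 80.3% |
| 7.5 | 167 | 160 | 74.7% | 81.3% | 160 | 74.7% |

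**3. Allowing for sampling error in 40 pairs.** 200,000 simulated interims per SD, normal differences with mean -1.7, all 40 pairs taken as observed, same rule:

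| True SD | Mean N, without / with /0.85 | Power at 85% evaluable, without / with | Power if all contribute, without |
|---|---|---|---|
| 6.0 | 124 / 134 | 81.9% / 84.4% | 87.7% |
| 6.5 | 132 / 144 | 78.0% / 81.3% | 84.3% |
| 7.0 | 142 / 152 | 74.9% / 77.9% | 81.4% |
| 7.5 | 150 / 156 | 71.6% / 73.6% | 78.4% |

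The omission changes N in 43% to 71% of interims.

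**4. Raw-count scale.** Write the Week 24 left-right count difference as the baseline difference (SD b, mean zero) plus the difference in change. Its variance is b² + SD² + 2 x rho x b x SD. The documents give neither b nor rho. Assumed ranges: b from 2 to 8 and rho from -0.5 to 0.3. Protocol 5.3.2 allows up to 2:1 asymmetry (20 against 10 scars is a difference of 10), so a large b cannot be ruled out.

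*Only imputed values raw, 15% of 40 (6 subjects), SD 6.0, N otherwise 118:*
- b = 2, rho = -0.5: 0.85 x 36 + 0.15 x 28 = 34.8; (40/39) x (34.8 + 2.89) = 38.66; N_recalc 107, so N = 118.
- b = 8, rho = 0.3: 0.85 x 36 + 0.15 x 128.8 = 49.92; (40/39) x (49.92 + 2.89) = 54.16; N = 150.
- With b limited to 2-4, N is 118 to 123.

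At larger SDs the shift can go either way: 124 to 160 at SD 6.5 (otherwise 128) and 142 to 160 at SD 7.0 (otherwise 147).

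*All values raw, SD 6.0:*
- b = 3, rho = -0.5: variance 27, N_recalc 86, so N is the floor of 118.
- b = 4, rho = 0.3: variance 66.4, N_recalc 195, so N is the cap of 160.

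**5. Units.** If the floor is 100 rather than 118 and N came out at 100, then 85 evaluable subjects give 73.3% power at SD 6.0. The cap equals 136/0.85 = 160, where 136 is the formula result at SD 7.0. That hints that the cap is in randomised subjects, but the SAP does not say so.

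**The case against.** **Loose wording.** The imputation sentence may be shorthand, with change from baseline meant throughout; inheriting delta and SD from SAP 4 points that way. This stands as far as it goes, and is why the firm finding is that X is undefined. A reader might infer that raw imputed values are definitely mixed with change-score observed values. SAP 4.1 never says the observed values are change scores, so mixing is one reading and raw counts throughout is another. A reader might also infer that the scale effect is small. That holds for a baseline SD of 2 to 4, a range with no source in the documents.

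**Blinding.** A reader might infer that citing 6.3.6.2 forces imputation by treatment and so breaks the blind. It does not: SAP 4.1 imputes one squared difference per subject, which has no treatment group to split by. The cross-reference simply does not settle the scale.

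**The power loss is overstated.** The primary analysis keeps all randomised subjects with multiple imputation, and SAP 3.2.4 encourages those who stop study drug to attend remaining visits. This stands. 85% evaluable is a lower limit, and at 92.5% effective information power is 80.4% at SD 6.5 and 80.3% at SD 7.0. Still, Table 8 counts the 15% as lost, and SAP 4.1 does not explain why it stops doing so.

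**The uncentred estimator compensates.** In part: it adds about 1.7² = 2.89 to the variance, 8% at SD 6.0. Ignoring this and plugging in the true SD would suggest power of 73.6% at SD 6.5 and 73.7% at SD 7.0. The SAP's own estimator does not support so large a loss, and the tables above already include the offset.

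**Conclusion.** Both points hold and should be fixed.

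- **Scale.** X needs a definition, and the imputation sentence is on the wrong scale for the endpoint. Neither size nor direction of the effect on N can be known from the documents. For context, sampling error alone puts N_recalc between 74 and 153 (5th to 95th percentile) at SD 6.0.
- **Dropout.** With floor 118 there is no harm at SD 6.0. At SD 6.5 to 7.0, where the re-estimation is meant to act, power at the expected N is about 77% if 15% contribute nothing and about 83% if everyone contributes. Averaged over interims, the omission costs about 2 to 3.5 points. At SD 7.5 the cap binds at the expected N either way.
- **Floor.** Whether N_init is 100 or 118 must be stated; the figures above assume 118.

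Type I error is unaffected, and with that floor N stays between 118 and 160. The documents do not show that the trial is underpowered or that a wrong N was used. They show that the rule cannot be programmed without choosing a reading, and that it can miss its own 80% target.

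**What to change.** Amend SAP 4.1:

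(a) Define LR_j = (Week 24 - baseline) on the left minus (Week 24 - baseline) on the right.

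(b) Impute on that scale while blinded, and square afterwards. Either impute the signed LR change difference per subject from its earlier values, or impute left and right counts jointly in one model. Do not impute separately by treatment group or by side. Separate models by side lose the within-subject correlation: at SD 6.0 with 15% imputed, an assumed side correlation of 0.5 to 0.7 and 30% to 60% of variance explained, N_recalc would rise from 111 to between 117 and 135.

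(c) State N_init, N_recalc and N_max in the same units, with N_init = 118 randomised. Then either use N = min(160, max(118, ceil(N_recalc/0.85))), or keep the present rule, say that the allowance is left out deliberately because the uncentred estimator and multiple imputation partly offset it, and give the resulting power range.

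If the re-estimation has already been run, recompute it blinded and report both results.

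**Cost.** A few lines of SAP text and a blinded re-run on data already held; the re-run may give an N different from the one used. The /0.85 option adds about 10 subjects on average at SD 6.0 (124 to 134), where the target is already met.
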